**NCT03870048 tDCS to Lower Neuropathic Pain and Fatigue in People With Multiple Sclerosis**

Prospective participants, men and women with MS, will be recruited. To accomplish this study, 20 participants will need to complete 3 randomly-ordered blocks of protocols (sham, 2 mA, 4 mA), separated by at least one week. Each block involves 5 daily sessions at the INPL. The duration of each session will be approximately one hour and will be completed at the same time of day for each subject. We expect data collection to last 6 months. Each session will be a combination of questionnaires, leg strength assessment, and an isokinetic fatigue test.

Leg strength assessment: Isokinetic (concentric/concentric) flexion and extension of the knee at 60°/s will be performed five times to determine the more-MS affected leg. When strength difference between the left and right legs is less than 10%, the more affected side will be based on the participant's self-report.

Isokinetic fatigue test: Participant's will perform 40 consecutive repetitions of isokinetic concentric/concentric flexion and extension of the knee on the more-affected leg at 120 degree/sec.

In the initial session (i.e., Block 1, Session 1) subjects will 1) be consented, 2) complete the Patient Determined Disease Steps (PDDS) questionnaire, 3) the Fatigue Severity Scale (FSS), 4) Neuropathic Pain Questionnaire (NPQ), 5) Visual analog scale (VAS), 6) perform a leg strength assessment, 7) perform an isokinetic fatigue test, and 8) undergo either sham tDCS, tDCS at 2 mA, or tDCS at 4 mA, depending on the randomized block.

tDCS treatment protocol: A tDCS device (Soterix) will deliver a small direct current through two sponge surface electrodes (5cm × 5cm, soaked with 15 mM NaCl). The positive electrode will be placed over the motor cortex representation of the more affected leg, and a second electrode will be placed on the forehead above the contralateral orbit. The three protocols blocks (sham, 2 mA, 4 mA) will be performed in randomized order.

tDCS Block: The participant will receive tDCS for 20 min at an intensity of 2 mA or 4 mA while seated comfortably and quietly in a room. The intensity will start at 0 mA and will be incrementally increased to 2mA or 4 mA over the initial 30 seconds. At the 19:30 minute time point, the current will gradually be reduced from 2 mA (or 4 mA) to 0 mA.

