**STATISTICAL ANALYSIS** The generalized estimating equation (GEE) framework will be utilized to assess changes over time in fatigue and quality of life measures. An interaction term between time and treatment will allow us to test the within and between-treatment differences over all time points. Using histograms, variable distributions will be assessed to decide which link function to specify when modeling each outcome. To account for the inherent correlation that occurs in repeated measures data, we will cluster on subject ID. In addition to examining the unadjusted relationship between the time-treatment interaction and each outcome, we will consider the addition of control variables, which will reduce the likelihood of unaccounted confounders. The control variables being considered for inclusion in the adjusted models are age, sex, and time since discharge/discontinuation of home isolation. For each outcome, models will be fit for all possible combinations of control variables. The predictor set that yields the smallest Akaike information criterion (AIC) will be considered the optimal control variable set to adjust associations between the main predictor and the outcomes. Statistical significance will be assessed at the  $\alpha = 0.05$  level. Analyses will be conducted using SAS 9.4.

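### The link function for each outcome is chosen from histograms, which cannot identify it, so the scale of the time-by-treatment effect is not fixed in advance

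*Combined protocol and SAP*

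**What the plan says.** The Statistical Analysis section plans a GEE analysis: "The generalized estimating equation (GEE) framework will be utilized to assess changes over time in fatigue and quality of life measures". The inferential target is an interaction: "An interaction term between time and treatment will allow us to test the within and between-treatment differences over all time points". Correlation is handled by a single statement, "we will cluster on subject ID". The link is left to the data: "Using histograms, variable distributions will be assessed to decide which link function to specify when modeling each outcome".

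No candidate links, decision rule or default are given. The section does not say whether the histograms are pooled or split by treatment, whether the person viewing them is blinded, whether effects will be reported as differences or ratios, or whether another link will be tried as a sensitivity analysis. The only other data-driven modelling step is the AIC search over covariates ("For each outcome, models will be fit for all possible combinations of control variables"), which does not restrict the link.

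The design is a three-period crossover: "20 participants will need to complete 3 randomly-ordered blocks of protocols (sham, 2 mA, 4 mA), separated by at least one week". On timing, "Each block involves 5 daily sessions at the INPL".

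**The concern.** The link sets the scale on which the mean responds to time and treatment. The shape of the raw scores is a different matter: it reflects largely how people differ from one another, and it bears on the distribution or variance function. A skewed histogram is compatible with an identity link and a symmetric one with a log link. Two analysts could therefore follow the plan faithfully and fit different models.

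This matters more than usual because the tested term is an interaction, and interactions depend on scale. With identity, the interaction is a difference between treatments in change in score. With log, it is a ratio of ratios. At stake are the meaning of the reported effect, whether outcomes can be read side by side, and in some trials whether the result is called significant.

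**Working it through.** **Inputs from the documents.** 20 participants, 3 blocks and 5 sessions per block (opening paragraph); clustering on subject and significance level 0.05 (Statistical Analysis). A full interaction over five sessions has (3 − 1) × (5 − 1) = 8 degrees of freedom. The plan gives no error rate for the link rule and no power, effect size or SD, so it has no figure of its own to reproduce.

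**Assumptions, not in the documents.** Two-sided testing; identity and log as the candidate links; the histogram rule read as choosing log when pooled skewness exceeds 0.75; complete data; lognormal or normal scores with the SDs shown below.

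**Step 1: scale, by arithmetic.** The identity interaction is (change on active) − (change on sham). The log interaction is (end/start on active) ÷ (end/start on sham).

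- Sham 40 to 36, active 50 to 45. Identity: −5 − (−4) = −1. Log: 0.90 ÷ 0.90 = 1, no interaction.
- Sham 60 to 48, active 40 to 30. Identity: −10 − (−12) = +2, favouring sham where lower is better. Log: 0.75 ÷ 0.80 = 0.9375, favouring active. The sign reverses.

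Both examples need unequal starting levels. If both blocks start at the same mean B and end at S (sham) and A (active), the identity interaction is A − S and the log interaction is A/S. One is null exactly when the other is, so with equal expected baselines the two links share the same null.

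**Step 2: unequal starting levels.** Let sham fall from 50 to 40 and let the active block also fall by 10, from a start 0, 5, 10 or 20 units lower. The identity interaction is 0 throughout. The ratio of ratios at an offset of 10, for example, is (30/40) ÷ (40/50) = 0.9375. Simulation with normal data, one contrast and an F-type small-sample correction gives:

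| Baseline offset | Ratio of ratios | Identity rejects | Log rejects | Links disagree |
|---|---|---|---|---|
| 0 | 1.00 | 4.8% | 4.5% | 1.0% |
| 5 | 0.972 | 4.4% | 6.3% | 5.1% |
| 10 | 0.9375 | 4.1% | 13.0% | 12.4% |
| 20 | 0.833 | 5.2% | 38.7% | 40.5% |

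These rows show how far the links can part. They are not the error rate of the plan's rule: with these normal data the skewness rule chose log in about 1% of trials or fewer.

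**Step 3: no treatment effect, equal baselines.** Two conditions by two times, 20 people, lognormal scores, t reference:

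| Log-SD between / within person | Identity | Histogram rule |
|---|---|---|
| 0.3 / 0.15 | 4.8% | 5.2% |
| 0.5 / 0.35 | 4.7% | 6.5% |
| 0.8 / 0.5 | 3.7% | 8.7% |

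Normal data show no gap. At 0.3/0.15 the rule picks log in about half of trials.

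In the full 3 × 5 design (between-person SD 0.3-0.4, within-person 0.15-0.2, skewed data, F-corrected), rejection for identity, log, the histogram rule and the better of the two p-values is 4.3, 5.8, 5.8 and 5.9% at 1 df, and 4.2, 9.7, 9.0 and 10.0% at 8 df. The histogram rule lies between the two fixed links or level with the higher. Deliberately taking the better p-value adds only 5.9 − 5.8 = 0.1 and 10.0 − 9.7 = 0.3 points to the log link. The rise therefore belongs to the log-link Wald test with 20 clusters.

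**Step 4: true effect.** In the two-by-two setting with a true 10-30% reduction, the links disagree on significance in about 1-13% of trials across the assumed spreads.

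**Step 5: what fixing the link leaves undone.** With identity fixed but no small-sample correction, the sandwich test in the 3 × 5 design still rejects a true null in about 7-9% of trials at 1-2 df and about 40% at 8 df (normal data). With the correction it is 4.5-5.2%.

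**The case against.** The strongest reply starts from the design. This is a within-person crossover in random order, and in Session 1 the FSS and NPQ come before stimulation. Without carryover, block baselines are equal in expectation and absence of interaction means the same thing under both links. A reader might infer that the tested hypothesis itself is left open. The documents do not support that. The effect measure is open, and the hypotheses part only with carryover; chance baseline imbalance can make the fitted interactions differ even when the null is shared. This part of the reply stands.

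A reader might also infer that choosing from histograms works like picking the better p-value and so inflates false positives. The plan does not say that. A pooled histogram does not select on the test result, and the excess under strong skew comes from few clusters. The larger gaps need very wide spreads that no document supplies; at log-SDs 0.3/0.15 the gap is 0.4 points. This part also stands.

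Nor does the plan say that histograms will be viewed by treatment or unblinded. Finally, different scales for a questionnaire and a strength test are not an error in themselves, and an identity link for every outcome is a preference.

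None of this rescues the rule. Even when pooled and blinded, a raw histogram does not tell the analyst which link is right.

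**Conclusion.** The concern holds for the effect scale. The plan ties the link, and with it the meaning of the interaction, to a display that cannot identify it, separately for each outcome. The links part under chance baseline imbalance, carryover or a true effect, and in the last case they disagree on significance in about 1-13% of simulated trials.

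The effect on error rate depends on assumptions and is secondary: from 0.4 points (5.2 − 4.8) to 5.0 points (8.7 − 3.7) under assumed skewed data with one contrast, and almost nothing for normal data. It should not be reported as inflation caused by the act of choosing. All simulated figures rest on SDs, candidate links and a skewness cut-off that the documents do not give, so they show direction and range only.

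This is a minor point, worth correcting because correction is cheap.

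**What to change.** Replace the histogram sentence with one that names, for each outcome and before outcome data are seen, the link and the effect scale. Identity, giving a mean difference in score, is a sound default for FSS and NPQ. For the isokinetic fatigue test, first define the summary measure, which the documents do not do, then state its scale. Use residuals of the fitted model only as a check that does not change the main analysis. Report the alternative link or a within-subject permutation test as a pre-specified sensitivity analysis.

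The cost is a sentence or two in the plan. If effects are truly proportional, identity loses about 0-5 points of size-adjusted power. The raw gap can reach about 13 points, but part of that is the log test's excess size. Any link named in advance would meet the point.

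Separately, add a small-sample correction for the 20-cluster sandwich test, because fixing the link does not by itself secure 5%.

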Sham block: Identical to the tDCS block, except the participants will only receive the initial 30 seconds of ramp-up, after which the current will be set to 0 for the remainder of the 20 minutes.

The remaining sessions of first block (i.e. Block 1, Sessions 2-5) will be as follows: In Sessions 2 and 4, the subjects get the tDCS or sham treatment, after which they will complete the fatigue and pain questionnaires (FSS and NPQ). Sessions 3 will be the same as Sessions 2 and 4, except that the isokinetic fatigue test will be performed at the beginning (i.e., before the tDCS or sham treatment). Session 5 will start with tDCS or sham treatment, then the isokinetic fatigue

test, and finally the fatigue and pain questionnaires.

Blocks 2 and 3 will be completed in the same manner as Block 1, except that the subjects will not redo the PDDS, VAS, and BDI in Session 1 and the treatment will shift to either tDCS at 2 mA, tDCS at 4 mA, or sham, depending on how the blocks were randomized. Block 2 will be randomly assigned based on uncompleted stimulation blocks.

Duration of Relief – If the participant indicates any reduction in pain following the previous day's tDCS session, they will be asked to estimate how long their pain was reduced following the session. Additionally, one week following the last testing session (i.e., Block 2, Session 5), participants will be contacted via telephone and asked the following questions:

1. Was tDCS effective at reducing your pain?
2. If so, how long did you notice a reduction in pain following your final tDCS session?
3. Have you reduced your use of pain relieving medications since your last tDCS session?

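### With 20 clusters, the GEE's stated 5% level depends on a test, variance estimator and time coding that the plan does not name

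*Combined protocol and SAP*

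**What the plan says.** The opening paragraph sets the number of independent units: "20 participants will need to complete 3 randomly-ordered blocks of protocols (sham, 2 mA, 4 mA"). Each block has five daily sessions.

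The STATISTICAL ANALYSIS section applies GEE to measures of fatigue and of quality of life. On the tested term it says: "An interaction term between time and treatment will allow us to test the within and between-treatment differences over all time points". On correlation: "To account for the inherent correlation that occurs in repeated measures data, we will cluster on subject ID". On the link: "Using histograms, variable distributions will be assessed to decide which link function to specify when modeling each outcome". On the level: "Statistical significance will be assessed at the" 0.05 level, in SAS 9.4.

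The session descriptions fix how many occasions enter each model. FSS and NPQ are completed in Session 1. In Sessions 2 and 4 participants are treated, "after which they will complete the fatigue and pain questionnaires (FSS and NPQ"), and Session 5 also ends with these questionnaires. For the third session, "Sessions 3 will be the same as Sessions 2 and 4, except that the isokinetic fatigue test will be performed at the beginning". The isokinetic test is therefore done in Sessions 1, 3 and 5. Blocks 2 and 3 drop only PDDS, VAS and BDI from Session 1, so FSS, NPQ and the isokinetic test keep a Session 1 value in every block.

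The section does not say whether time is categorical or linear, which working correlation is used, whether the variance is model-based or robust, which test is used, or whether any small-sample reference applies.

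**The concern.** Robust (sandwich) GEE inference is justified by a large number of clusters. Here there are 20, however many sessions each contributes. The sandwich covariance of p contrasts is estimated from only 20 subject-level vectors. A chi-square reference ignores that estimation error, and the damage grows with p.

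Two robust tests that both fit the plan's wording can then behave in opposite ways. A Wald test would declare effects too often. A score test would be close to nominal for one or two df but very conservative for many, and could miss a real effect. Because nothing is fixed in advance, the same data could be called significant or not according to a choice made at analysis. A model-based variance does not remove the problem, because it is valid only if the working correlation is right.

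**Working it through.** **Figure to reproduce.** The plan gives no power or sample-size calculation. Its only related figure is the nominal 0.05, so the question is whether each available test attains it.

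**Inputs from the documents.** n = 20 subjects, three conditions, five questionnaire sessions per block and three isokinetic sessions per block. Interaction degrees of freedom:
- one contrast: p = 1
- linear time, or pre/post, by three conditions: p = 2
- isokinetic test, categorical sessions: p = (3-1)(3-1) = 4
- five-session questionnaire, categorical sessions: p = (3-1)(5-1) = 8

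**Formula.** Assume complete data, an identity link and normal within-subject contrasts. The interaction estimate is the mean of n subject-level contrast vectors, and the uncorrected sandwich is their covariance with divisor n. Then W = [np/(n-p)] F(p, n-p), and the robust score statistic is S = W/(1 + W/n). With c the 95% chi-square point on p df:
- Wald size = P{F(p, n-p) > c(n-p)/(np)}
- Score size is the same expression with c replaced by c/(1 - c/n)

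No variance has to be assumed. For p = 8, c = 15.51. The Wald threshold on F(8,12) is 15.51 x 12/160 = 1.163, where the correct 5% point is 2.849. For the score test, 15.51/(1 - 15.51/20) = 69.0, which is 5.18 on the F scale.

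| p | c | F threshold, Wald | Wald size | F threshold, score | Score size | Correct F 5% point | Correct cut-off for W |
|---|---|---|---|---|---|---|---|
| 1 | 3.84 | 3.649 | 7.1% | 4.517 | 4.7% | 4.381 | 4.61 |
| 2 | 5.99 | 2.696 | 9.5% | 3.849 | 4.1% | 3.555 | 7.90 |
| 4 | 9.49 | 1.898 | 16.0% | 3.610 | 2.8% | 3.007 | 15.03 |
| 8 | 15.51 | 1.163 | 39.3% | 5.178 | 0.6% | 2.849 | 37.98 |

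A covariance divisor of n-1 gives Wald sizes of 6.48, 8.49, 14.35 and 36.28%, so the divisor is not the main cause.

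**Simulation of the Wald test.** With 20,000 runs of normal data, the sizes were about 7.1% (1 df), 9.2-9.4% (2 df), 15.6% (4 df) and 39.4% (8 df). At 8 df, adding age and sex gave 40.2% and skewed errors with an identity link gave 39.7%.

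**Check of the F and t references.** Identity-link GEE with a period term was fitted under assumed SDs (subject 1, block 0.5, error 0.7 with AR(1) 0.5). Between 0 and 10% of visits were missing, and the working correlation was independence or exchangeable (8,000 runs per setting).
- 8 df: chi-square 37.6-39.2%, F 4.1-5.2%
- 4 df: chi-square 14.4-17.0%, F 4.3-5.5%
- 1 df: z 6.7-7.5%, t 4.7-5.4%

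A separate check with only 500 runs per case gave 4.2-7.0% for F. Its Monte Carlo standard error is sqrt(0.05 x 0.95/500) = 1.0 percentage point.

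**Log link.** With an assumed lognormal outcome and a log link (20,000 runs), F gave 14.8% at 8 df and 10.2% at 4 df, and t gave 6.5-6.6%. A re-randomisation p-value, with six block orders equally likely, gave 4.2-5.4% (3,000 runs).

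**Interval width.** t(0.975, 19)/1.96 x sqrt(20/19) = 2.093/1.960 x 1.026 = 1.096.

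**Power of joint tests.** If t(19) on one contrast has 80% power, its noncentrality is 8.72. Holding that value gives 68% for F(2,18), 51% for F(4,16) and 30% for F(8,12). These are lower bounds, because correlated contrasts usually raise the joint noncentrality. Under the same assumed SDs, calibrate the 4 mA minus sham change from Session 1 to Session 5 to 80% on t(19):
- only 4 mA at Session 5 differs: 81% (2 df), 82% (4 df), 77% (8 df)
- 4 mA departs linearly over the block: 65% (4 df), 41% (8 df)
- the same, with 2 mA departing half as much: 51% (4 df), 31% (8 df)

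**The case against.** The strongest objection is that the plan never commits to a chi-square Wald test. A reader might infer from the table that the planned analysis has a 39% false-positive rate. The documents do not support that: no variance, test or SAS procedure is named, and a score test would err the other way. Nor do they support a claim that inflation is the likely direction. This part of the objection stands, and the point is worded accordingly.

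The 8-df test is also only one possibility. Testing differences within and between treatments fits individual contrasts at least as well as an omnibus test, and for one contrast the Wald inflation is modest, 7.1% against 5%. That also stands.

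The set of outcomes is not clear either. The analysis section speaks of fatigue and quality of life; it does not mention pain and names no quality-of-life instrument. The 8-df case applies to FSS, and to NPQ only if NPQ is analysed by this GEE.

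Finally, a reader might infer that joint tests are necessarily weak here. The 68/51/30% figures are a floor, and the actual power depends on the effect pattern.

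None of this supplies the missing specification. Even the mildest Wald case exceeds the stated level, and the spread between two admissible tests, 2.8% to 16.0% at 4 df and 0.6% to 39.3% at 8 df, is itself the problem.

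**Conclusion.** The concern holds as under-specification with a measurable consequence. With 20 clusters, large-sample robust GEE inference does not deliver the stated 5%. A chi-square Wald test runs from 1.4 times nominal (7.1/5) for one contrast to 7.9 times (39.3/5) for an 8-df omnibus test. A score test runs from near nominal to 0.6%. Until the test and its reference are named, the stated alpha does not have a defined meaning.

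The sizes are exact for 20 complete subjects, normal contrasts and an identity link, and need no variance assumption. The missing-visit, log-link and power results rest on assumed SDs and distributions. No size is given for model-based variance, because the documents report no variances from which to compute one. How alpha is shared between contrasts and outcomes is a separate question, not settled here. The point should be fixed before analysis.

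**What to change.** Keep the time-by-treatment GEE and add to the STATISTICAL ANALYSIS section:

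1. The coding of time for each outcome, the working correlation and a robust variance, and which outcomes (NPQ in particular) are analysed this way.
2. Main inference on prespecified single contrasts: each active condition versus sham, in change from Session 1. Multiply the robust z by sqrt((n-1)/n) and refer it to t with n-1 df.
3. For any joint test on p df, refer W(n-p)/(np) to F(p, n-p).
4. n is the number of subjects analysed, and cut-offs are recomputed for it. The n = 20 cut-off of 37.98 at 8 df would have size 12.1% at n = 16.
5. If the histograms point to a skewed outcome, either analyse it log-transformed with an identity link, or take the p-value from re-randomising each participant's block order under the actual allocation scheme. The design provides the basis for the latter: "The three protocols blocks (sham, 2 mA, 4 mA) will be performed in randomized order". The F reference alone is not adequate for a log link on skewed data.

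The cost is SAP wording and a few lines of code, with no new data. With complete data and an identity link the estimates do not change, and the 95% interval for a contrast is about 9.6% wider at n = 20. A log transform changes the effect to a ratio of geometric means. The re-randomisation p-value tests the hypothesis that no condition has any effect. A joint test may have less power than a well-chosen single contrast, which is a reason to put the contrasts first.

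### The plan selects GEE covariates by AIC, which GEE does not have (minor effect), and names no test, time coding or small-sample method for 20 clusters, so the true error level is undetermined in both directions

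*Combined protocol and SAP*

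**What the plan says.** The combined document's STATISTICAL ANALYSIS section sets the model: "The generalized estimating equation (GEE) framework will be utilized to assess changes over time in fatigue and quality of life measures". The tested term is the time-by-treatment interaction: "An interaction term between time and treatment will allow us to test the within and between-treatment differences over all time points". Correlation is handled by clustering: "To account for the inherent correlation that occurs in repeated measures data, we will cluster on subject ID". The link is left to the data: "Using histograms, variable distributions will be assessed to decide which link function to specify when modeling each outcome".

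An unadjusted analysis is planned ("In addition to examining the unadjusted relationship between the time-treatment interaction and each outcome"), and then an adjusted one. The candidates are named: "The control variables being considered for inclusion in the adjusted models are age, sex, and time since discharge/discontinuation of home isolation". The search is exhaustive: "For each outcome, models will be fit for all possible combinations of control variables". The choice is by AIC: "The predictor set that yields the smallest Akaike information criterion (AIC) will be considered the optimal control variable set". The level is 0.05 and the software is SAS 9.4. No procedure, standard-error type, test statistic, reference distribution or coding of time is given.

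The protocol's opening paragraph requires 20 completers, each taking sham, 2 mA and 4 mA in random order, with five sessions per block. From the descriptions of the sessions, the FSS is completed at all five sessions of a block and the isokinetic fatigue test at Sessions 1, 3 and 5.

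**The concern.** There are two separate issues.

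First, AIC is built from a maximised likelihood, and GEE specifies none. An AIC could be taken from an independence likelihood, but that ignores the within-person correlation that the clustering is there to handle. The stated purpose, protection against confounding, does not apply to age and sex when each person serves as their own control. The third candidate matches no event in the protocol: no hospital discharge or isolation period is described, so the variable appears not to apply to this trial.

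Second, the usual robust GEE tests rely on a large number of clusters, and here there are 20. How far the true level departs from 5% depends on the test and on its degrees of freedom, and the plan fixes neither. At stake are the false-positive rate, the coverage of intervals and, through the coding of time, the power.

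**Working it through.** **Inputs.** n = 20 clusters, three conditions and five sessions (protocol, opening paragraph); isokinetic test at three sessions; alpha 0.05 (STATISTICAL ANALYSIS). Assumed, because not stated: two-sided tests, complete normal data, identity link. The plan gives no effect size, SD or power behind the 20, so there is no figure of its own to reproduce beyond the nominal 0.05.

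**Degrees of freedom the interaction could have.**
- One named contrast: 1.
- Linear time: (3−1)×1 = 2.
- Categorical time, isokinetic test: (3−1)×(3−1) = 4.
- Categorical time, FSS: (3−1)×(5−1) = 8.

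Applying the 8-df case to the NPQ would be an inference, since the section names only fatigue and quality of life.

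**Level of the two uncorrected tests.** With balanced complete data the GEE estimate is the mean of per-person contrasts. The uncorrected robust Wald statistic is then W = [nq/(n−q)]·F(q, n−q), and the robust score statistic is S = nW/(n+W). With c the 95% point of chi-square on q df:
- Wald level = P{F(q, n−q) > c(n−q)/(nq)}.
- The score test rejects when W > nc/(n−c). Its level is the same expression with nc/(n−c) in place of c.

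| q | c | Wald: F cut-off | Wald level | Score: W cut-off | Score level | W cut-off for a true 5% |
|---|---|---|---|---|---|---|
| 1 | 3.84 | 3.65 | 7.1% | 4.75 | 4.7% | 4.61 |
| 2 | 5.99 | 2.70 | 9.5% | 8.55 | 4.1% | 7.90 |
| 4 | 9.49 | 1.90 | 16.0% | 18.05 | 2.8% | 15.03 |
| 8 | 15.51 | 1.16 | 39.3% | 69.03 | 0.6% | 37.98 |

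Simulated GEE fits with exchangeable working correlation (800 to 1,000 trials) gave Wald levels of 8.9%, 13.3% and 37.8% at 2, 4 and 8 df. The 4-df value is a little over two Monte Carlo standard errors below the exact 16.0%; the others agree.

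**Intervals, single contrast.** In units of the usual standard error, the robust-z half-width is 1.960×√(19/20) = 1.910, against 2.093 for t on 19 df. The ratio is 0.913, so the interval is 8.7% too narrow, and coverage is P(|t19| < 1.910) = 92.9%.

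**Covariate search.** Three candidates give 2³ = 8 models per outcome. A covariate that is constant within a person is balanced over that person's condition-by-session cells. With complete data and an identity link it therefore leaves every treatment contrast unchanged, and simulated adjusted and unadjusted fits agreed to rounding error. Selection by an independence AIC over three person-level covariates (4,000 null trials) gave the following uncorrected Wald levels:
- Complete data: 39.8% with and without selection at 8 df, and 7.05% with and without at 1 df.
- 10% of sessions missing: 38.2% unadjusted and 40.7% after selection at 8 df (2.5 points); 6.6% and 7.4% at 1 df (0.8 point).

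**Power and the coding of time.** Take valid F tests and an effect with noncentrality 11.43.
- Linear effect: power is 80% on F(2, 18) and 40% on F(8, 12).
- Step after Session 1, pattern (0,1,1,1,1), independent residuals: the squared correlation with linear scores is 2²/(10×0.8) = 0.5. Linear time then retains noncentrality 5.715 and power 49%, against 40% on 8 df.

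**The case against.** The strongest reply is that the plan never specifies an uncorrected Wald test. A reader might infer that the trial has a false-positive rate of 39%. The documents do not support that: the figure needs categorical time, an uncorrected Wald test and the 8-df interaction as the deciding test, and none of the three is stated. A score test complies equally well with the text and errs the other way. On the mildest reading, a single contrast, the excess is about 2 points. This reply stands as to direction. It does not remove the gap, because under the assumptions above neither uncorrected test attains 5% in any of the four cases.

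A reader might also infer that the AIC search distorts the treatment result. It does not do so materially. With complete data and an identity link, person-level covariates change nothing, and the unadjusted analysis is planned in any case. No figure should be built on the home-isolation variable, because the protocol does not define it.

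Finally, linear time might look like the obvious way to keep power. That holds for a roughly linear effect. The Session 1 questionnaires precede the first stimulation of a block, while those of Sessions 2 to 5 follow that day's stimulation, so a step is at least as natural, and then the gain is small.

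**Conclusion.** The point holds in two parts of unequal weight. Selection by AIC is wrong as written, but it is a wording matter: no effect with complete data and an identity link, and roughly 1 point of level at 1 df and up to about 2.5 points at 8 df with 10% of sessions missing.

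The missing test specification carries the weight. Analyses that all comply with the text have true levels from 0.6% to 39.3%, so the error rate is undetermined, not shown to be inflated. These values are exact for complete normal data, an identity link and 20 clusters. Because the link is to be chosen from histograms, other cases can arise: with a log link and lognormal data (assumed CV about 53%), the uncorrected Wald test ran at about 8-9%, 12%, 20% and 48% for 1, 2, 4 and 8 df.

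**What to change.** **Covariates.** Drop the all-subsets search and fix the set in advance; none is acceptable. If a search is kept under GEE, use QIC. Remove the home-isolation covariate unless it is defined for this trial.

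**Deciding test.** State how time is coded and one deciding between-treatment contrast or low-df interaction. Justify the coding by the expected time course.

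**Small-sample method.** Name one, confined to what it covers:
- (a) *Identity link.* Kauermann-Carroll sandwich, with t on 19 df for single contrasts within or between treatments. For a q-df interaction, multiply that Wald statistic by (n−q)/(q(n−1)) and refer it to F(q, n−q). Using F(q, 19) instead is not enough: 23.4% at 8 df. With a log link, (a) ran at 6-9% for moderate skew, and up to 22% at 8 df for extreme skew (CV about 131%).
- (b) *Identity link.* Mixed model with subject and subject-by-block effects and Kenward-Roger df. The 8-df test ran at 5.0%, but at 6.0-6.5% with AR(1) 0.5 residuals within block, unless that correlation is modelled.
- (c) *Any link, between-treatment tests only.* A randomisation test that re-permutes the conditions over each participant's blocks, keeps a block's sessions together and follows the actual scheme. Simulated levels were 4.5-6.0%. Use a studentised statistic for pairwise contrasts: with only the third condition active, an unstudentised one rejected in 0.2-0.4% of trials, against about 5-6% studentised. It does not test within-treatment change over time.

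**Cost.** A few sentences, plus a short program for (c). Single-contrast intervals widen by about 10% (2.093/1.910 = 1.096) relative to robust-z. Apparent power falls relative to the uncorrected Wald test, most at 8 df, where the critical value rises from 15.51 to 37.98.
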